## **4. RESEARCH DESIGN**

This is a retrospective single-center cohort study.

## **5. ELIGIBILITY CRITERIA**

### **5.1. Inclusion criteria**

- Patients operated on for posterior-stabilized total knee arthroplasty between January 2015 and December 2018
- unilateral arthroplasty
- a known address for mailing the study information letter

### **5.2. Exclusion criteria**

- revision arthroplasty
- patients who refused to the use of their data

### **5.3. Feasibility and recruitment procedures**

Perioperative arthroplasty data will be collected from medical records.

Five orthopedic surgeons performed total knee replacements.

The inclusion period last from January 2015 to December 2018.

## **6. RESEARCH STRATEGY(IES)/ PROCEDURE(S)**

Three phases:

### **Phase 1**

The traditional care consisted of patients attending a surgical consultation during which the date of the operation was scheduled, followed by a pre-operative anesthesia consultation. Patients at risk of postoperative nausea and vomiting were screened and given multimodal prophylaxis and treatment. In case of anemia, erythropoietin was injected preoperatively[8]. Tranexamic acid was given by intravenous injection to reduce perioperative blood loss[9]. Patients received antimicrobial and antithrombotic prophylaxis treatment. Normal body temperature was maintained perioperatively[10]. During surgery, a femoral nerve block was placed for postoperative pain management. At the end of the operation, one or two drains were put in place to evacuate the blood and avoid post-operative hematomas. A Zimmer knee brace was used to immobilize the knee. Postoperative analgesia was provided by the self-controlled administration of local anesthetics via the femoral nerve catheter, and supplemented by systemic analgesics (paracetamol, oxycodone, nonsteroidal

anti-inflammatory drugs in the absence of contraindications). The first mobilization took place with the orthosis at day one or day two after surgery.

## **Phase 2**

By the end of 2016, several operative and post-operative modifications were set up. Femoral nerve block was replaced by adductor canal block in combination with local infiltration analgesia[11], which has been shown to provide equivalent analgesia, while preserving quadriceps motor strength[12]. Zimmer Knee Splints was replaced by compressive cryotherapy knee brace for pain and bleeding management[13]. Only, one drain was used to evacuate the blood and avoid post-operative hematomas. The first mobilization happened at day zero, assisted by an Artromot®[14].

## **Phase 3**

To complete this program, from 2018 onwards, educational therapy with a nurse has been added. Patients were more comprehensively informed about the global care pathway. If necessary, counselling to assist with smoking cessation and addiction[15] could be offered in order to reduce risk of postoperative complications. Nutritional care could be set up on demand. If patients wished to be discharged to a rehabilitation center, the demand for beds was anticipated in order to reduce hospital waiting times. Operative and post-operative management was the same as before, except that draining was not systematic as it has not been used in well-documented hip and knee enhanced recovery programs, with no increase in complications[11].

## **7. CONDUCTING THE RESEARCH**

### **7.1. The research schedule**

Eligible patients are those who underwent total knee arthroplasty from January 2015 to December 2018.

### **7.2. Information of the persons concerned**

The doctor invites the patient to participate in this research and will inform him/her of:

- the objective,
- the digital processing of data concerning the patient that will be collected during this research and will also specify the patient's rights of access, opposition and rectification to these data.

## **8. STATISTICAL ASPECTS**

### **8.1. Calculation of study size**

According to the hospital information system, 470 patients were taken care for total knee arthroplasty surgery over the study period.

## 8.2. Statistical methods employed

Patients will be classified into three groups according to the type of care management they received: Phase 1, 2 or 3.

Means +/- standard deviations, counts, and percentages will be used to describe continuous and categorical variables, respectively.

Normal distributions will be verified and T-test or Mann-Whitney tests will be used to compare continuous data of independent samples where appropriate.

Chi-square test of homogeneity will be for categorical variables.

An alpha level of 0.05 will define statistical significance.

XLSTAT (Addinsoft) will be used for statistical analysis.

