## 1. SUMMARY OF THE RESEARCH

Title of the study	Single-center retrospective study on safety of total knee replacement surgery before and after the implementation of enhanced recovery program
Sponsor	Groupe Hospitalier de la Rochelle Ré Aunis
NCT number	NCT05028426
PI	[name]
Primary and secondary objectives	The objectives are to compare the number of adverse events at 1 month, the number of thromboembolic events, the average length of stay and the improvement of mobility before and after the implementation of rapid rehabilitation protocols after surgery
Methodology of reference (in France)	 MR-004  MR-005  MR-006
Data sources	 Medical records  Survey / Cohort / Register including data from the national health data system  Medicalization Program of Information Systems  Other source of Data
Study population	Patients over 18 years of age treated between 2015 and 2018 by the Orthopaedic Surgery and Traumatology Department of the Groupe Hospitalier de la Rochelle Ré Aunis for total knee replacement
Background	Enhanced Recovery After Surgery (ERAS) is a management method that aims to allow the patient to recover as quickly as possible their physical and mental capacities. It was initially developed for colon surgery and has recently been extended to orthopaedic surgery protocols.
Contexte of the study	This innovative method has been practiced by the Orthopaedic Surgery and Traumatology Department of the La Rochelle Ré Aunis Hospital Group since January 2017.
Methodology	Single center retrospective study

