Statistical analysis plan	
Epidemiological analysis :
 
 
- Description of Patients classified into three groups according to the type of care management they received: traditional care, some elements of a fast-track program during a transition period, and full enhanced recovery program.
 
- Using means +/- standard deviations, counts, and percentages to describe continuous and categorical variables, respectively
 
 
Comparative analysis of the three groups :
 
 
- Normal distributions will be verified and T-test or Mann-Whitney tests will be used to compare continuous data of independent samples where appropriate.
 
- Chi-square test of homogeneity will be used for categorical variables.
 
- An alpha level of 0.05 will be used for all statistical tests.
 

Justification of the public interest character of the study	Evaluation of the effectiveness and safety of a recent management protocol
Timetable for the study and provisional schedule for communicating the results	September 2019: drafting of the information leaflet, the protocol and the CRF From October 2019 to June 2020 : data collection End of 2020 : exploitation of the results and writing of a report/scientific manuscript

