## **2. SCIENTIFIC JUSTIFICATION**

Enhanced recovery programs are an organizational evolution in surgical patient management, in which the patient becomes an actor of his or her own recovery. This multimodal approach aims at optimizing patient physiological and psychological states across preoperative, intraoperative and postoperative domains of care. First described by Kehlet[1], these programs have been gradually modified and used for many surgery specialties, including the perioperative management of hip and knee replacements[2]. Convincing results for the benefit of the patients have been achieved in the reduction of perioperative complications, shorter hospital stays, and some improvements in quality of life (rapid restoration of physical and mental capacities)[3]. These programs also contributes to optimizing the production of care in light of human and material constraints, as they participate in 1) limiting the presence of patients in hospital by reducing the length of stay ; 2) a better control of the organization, with a better responsiveness to new challenges, like infection ; and 3) possible increase in the number of patients treated, which will be necessary according to various projections[4, 5].

Despite the proven benefits and numerous publications on enhanced recovery programs for total knee arthroplasty, physicians are still faced with the knowing-doing gap of translating the scientific data into daily clinical practice[6, 7].

In our center, the decision to take the step happened at the end of 2016. It was proposed by a young surgeon that have been trained on this new approach during his studies and who convinced the head of the surgery department of the benefits for the patients, the healthcare workers, and the institution. The transition took place in two stages, first operative and postoperative techniques were modified, and then preoperative education and counselling were added. Our hypothesis was that the shift from a traditional method of care to an enhanced recovery program can be implemented in a secondary-care hospital while ensuring the same safety and effectiveness for patients.

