## **3. OBJECTIVES**

### **3.1. Main objective**

The main objective is to measure early complication rate after total knee arthroplasty.

It will be determined by the number of patients with complication detected within 3 months after surgery.

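### Three non-randomised, largely successive care phases are compared by unadjusted tests only; preoperative motion is not used as an adjustment variable, and operating surgeon is not in the analysis

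*Combined protocol and SAP*

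**What the plan says.** Section 4 describes a retrospective single-centre cohort. Under section 8.2 patients are grouped by the care they received (phase 1, 2 or 3). By section 6, phase 2 care was set up by the end of 2016 and phase 3 care from 2018, so group follows calendar period closely.

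The inferential plan, in section 8.2 and again in the section 1 summary, consists of three elements: "T-test or Mann-Whitney tests will be used to compare continuous data of independent samples where appropriate", a chi-square test of homogeneity for categorical variables, and alpha 0.05. The summary also plans a "Description of Patients classified into three groups according to the type of care management they received". No regression, stratification, matching, weighting or covariate list appears.

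The aims are comparative. The summary wants to compare adverse events, length of stay and "the improvement of mobility before and after the implementation of rapid rehabilitation protocols after surgery", and justifies the study as "Evaluation of the effectiveness and safety of a recent management protocol". The section 2 hypothesis is that care can be changed "while ensuring the same safety and effectiveness for patients". The main outcome in section 3.1 is the "number of patients with complication detected within 3 months after surgery".

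Section 3.2 lists preoperative and postoperative flexion and extension as separate secondary measures. Section 5.3 says that five surgeons operated. Section 2 says of the change in care: "It was proposed by a young surgeon that have been trained on this new approach during his studies".

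**The concern.** A crude difference between phases mixes any programme effect with whatever else differed between the patients and surgeons of each phase. The protocol itself points to two such factors.

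- **Preoperative motion.** Surgery and rehabilitation cannot affect it, so it is a baseline value. It usually predicts postoperative motion. Improvement of mobility is an aim, but it is never defined as a change or as a baseline-adjusted difference. A table of patients by group would show an imbalance without correcting for it.
- **Operating surgeon.** With five surgeons, one of whom brought prior training in the new approach, each surgeon's share of operations could have changed between phases.

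A difference in either factor could produce an apparent programme effect or conceal a real one. Concealment deserves attention because the hypothesis is unchanged safety, so a non-significant crude test is likely to be read as reassurance.

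**Working it through.** The plan has no figure to reproduce: the 470 in section 8.1 is a count from the hospital information system, not the result of a formula. What follows is an illustration on assumed inputs.

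**Inputs from the documents.** 470 patients; January 2015 to December 2018, i.e. 48 months; changes of care at end 2016 and from 2018; alpha 0.05 (sidedness not stated, two-sided assumed). The 470 is not stated to be net of the eligibility criteria, so it is treated as an upper bound.

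**Assumed inputs.** Even accrual; equal SDs before and after surgery; pre-post correlation r of 0.3 to 0.7; preoperative difference d of 0.1 to 0.3 SD between phases; the surgeon rates and shares shown in step 3.

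**1. Phase sizes.** Phase 1: 470 × 24/48 = 235. Phase 3: 470 × 12/48 = 117.5, taken as 118.

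**2. Postoperative motion, phase 1 v phase 3, no programme effect.**
- SE in SD units = √(1/235 + 1/118) = 0.1128.
- Carry-over into the postoperative difference = r × d, from 0.3 × 0.1 = 0.03 SD to 0.7 × 0.3 = 0.21 SD.
- Noncentrality = 0.03/0.1128 = 0.27, and 0.21/0.1128 = 1.86.
- Rejection by the nominal 5% t-test (noncentral t): 5.8% and 45.9%. The middle case, r = 0.5 and d = 0.2, carries over 0.10 SD and rejects in 14.3%.
- With only 350 eligible patients (175 v 88), the ends of the range are 5.6% and 36.0%.

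A change score is not an automatic cure. Take d = 0.3 SD.
- If patients with equal baselines have equal expected outcomes in every phase, the covariate model is unbiased. The change score is then off by −(1 − r) × 0.3, i.e. −0.21 SD at r = 0.3 to −0.09 SD at r = 0.7.
- If instead the phases would have changed by equal amounts, the change score is unbiased. The covariate model is then off by (1 − r) × 0.3, i.e. 0.21 to 0.09 SD.
- Comparing postoperative values alone is off under both assumptions.

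The covariate also improves precision: residual variance is 1 − r², i.e. 0.91, 0.75 and 0.51 at r = 0.3, 0.5 and 0.7.

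**3. Complications, no programme effect.** Suppose lower-rate and higher-rate surgeons, with the lower-rate share rising between phases 1 and 3. Chi-square rejection is by exact enumeration at 235 v 118.
- Small shift (rates 8% and 12%, lower-rate share 0.2 to 0.3): 0.2 × 8% + 0.8 × 12% = 11.2%; 0.3 × 8% + 0.7 × 12% = 10.8%. Rejection is 4.9%, the same as with 11.2% in both phases.
- Large shift (rates 5% and 15%, lower-rate share 0.2 to 0.5): 0.2 × 5% + 0.8 × 15% = 13%; 0.5 × 5% + 0.5 × 15% = 10%. Rejection is 11.7%.

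**4. Complications, programme truly multiplies risk by 1.5.** Chance of a significant result in the direction of harm:

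| Shift | Phase 1 | Phase 3 if mix unchanged | Phase 3 with shift | Chance, mix unchanged | Chance with shift |
|---|---|---|---|---|---|
| Small | 11.2% | 16.8% | 16.2% | 32.2% | 27.2% |
| Large | 13% | 19.5% | 15.0% | 36.9% | 8.1% |

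Even with no shift, harm is missed in 100 − 36.9 = 63.1% to 100 − 32.2 = 67.8% of studies.

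**5. Room for covariates.** Phase (2 terms) plus five surgeons (4 terms) makes 6 terms. At a working rule of 5 events per term, that needs 30 events. Among 470 patients, a rate of 5% gives 23.5 events, 10% gives 47, 11.2% gives 52.6 and 13% gives 61.1. Whether surgeon can enter as five categories therefore depends on the observed event count.

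**The case against.** Four points can be made for the plan.

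**Scope and restriction.** Sections 3.1 and 3.2 speak only of measuring outcomes. Sections 5.1 and 5.2 restrict the cohort to unilateral, posterior-stabilised, non-revision arthroplasty at one centre. The restriction does limit case-mix, but it does not address surgeon, preoperative motion or calendar time. The summary and the hypothesis are plainly comparative.

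**Preoperative motion is measured.** A reader might infer that the plan ignores it. It does not: the values are listed, the tests of continuous data would cover them, and improvement of mobility may imply a change score. What is missing is their use as an adjustment variable.

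**No bias is shown.** A reader might infer that the results will be biased, or that surgeon mix would hide a rise in complications. The documents give no data by phase from which to conclude either. In the illustration the small surgeon shift adds no false positives, and the large shift is an extreme assumption. Most of the missed harm occurs with no confounding at all: it comes from limited precision and from testing for a difference, and adjustment does not cure that.

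**Adjustment has limits.** Phase and period largely coincide, so time trends remain. If the trained surgeon operated mainly in later phases, surgeons would overlap poorly across phases. A reader might also infer that propensity weighting is required for complications; the event counts in step 5 do not establish that.

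These objections limit the claim. They do not supply the missing adjustment.

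**Conclusion.** The point holds as a gap in the analysis plan that should be closed, not as evidence of bias. Unadjusted tests alone cannot support statements about the programme's effectiveness and safety when the groups are non-randomised and largely successive.

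The actual size is unknown. For motion, the illustration runs from negligible (6% rejection) to serious (46%), and rests on the assumed 235 v 118 split, equal SDs, r of 0.3 to 0.7 and an imbalance of 0.1 to 0.3 SD. For complications, only a large change in surgeon mix makes a material difference. The case is strongest for motion, where the baseline values are already on the list and adjusting for them also improves precision.

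**What to change.** **(a) Motion.** In section 8.2, compare postoperative flexion and extension between phases by a linear model with the preoperative value as covariate. Report mean change by phase beside it. Move the preoperative values from section 3.2 to a baseline table by phase. State that the two analyses rest on different assumptions in non-randomised groups, and report any disagreement between them.

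**(b) Complications and length of stay.** Report surgeon by phase. Where surgeon and basic patient factors such as age and sex can be retrieved, give an adjusted phase effect beside the crude result for 3-month complications and for length of stay. Prespecify few covariates and match their number to the observed events. Penalised logistic regression and propensity weighting are both acceptable for complications, and the choice can be left to the statistician. If these fields cannot be retrieved, state that as a limitation.

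**In either case,** state that phase and calendar time largely coincide, so adjustment does not remove time trends and the result is not proof of a programme effect.

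**Cost.** Part (a) uses variables already listed, but patients without a preoperative value drop out of the model. For part (b), the case report form is not among the documents, so what was recorded is unknown. The timetable reads "From October 2019 to June 2020 : data collection", so missing fields could mean reopening up to 470 records. Adjusted intervals may be wider than crude ones.

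### Length of stay and postoperative knee motion: three phases are to be compared with two-sample tests at 0.05, with no three-group test, no alpha control and no single before-and-after contrast

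*Combined protocol and SAP*

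**What the plan says.** Section 8.2 states: "Patients will be classified into three groups according to the type of care management they received: Phase 1, 2 or 3". The summary's analysis plan heads its list of tests "Comparative analysis of the three groups". For continuous data both places give the same instruction after a check of normality: "T-test or Mann-Whitney tests will be used to compare continuous data of independent samples where appropriate". On the significance level the summary adds: "An alpha level of 0.05 will be used for all statistical tests". Categorical variables get a chi-square test of homogeneity, which can take three groups.

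No ANOVA, Kruskal-Wallis test, trend test, regression, list of pairs, pooling rule or sharing of alpha appears anywhere in the document.

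Section 3.2 lists length of stay and knee extension and flexion, before and after surgery, as secondary objectives. The summary frames the aim as a comparison "before and after the implementation of rapid rehabilitation protocols after surgery". Section 8.1 gives one number, 470 patients, with no size per phase.

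**The concern.** The t-test and the Mann-Whitney test each compare two groups. A three-phase comparison made with them has to be a set of pairwise tests, or a comparison after pooling two phases. The plan does not say which, and it applies 0.05 to each test. If several tests are run on one outcome, 0.05 is no longer the chance of a false claim about that outcome.

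The before-and-after aim does not settle the matter, because implementation came in two steps. The data already exist, so a contrast left open now could be chosen with the results in view. A reader of the report could not tell whether it had been fixed beforehand.

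**Working it through.** **Step 1. Which contrast is before and after?**

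- The summary dates the method at the "Hospital Group since January 2017", and section 6 (Phase 2) puts the operative and postoperative changes at the end of 2016. This suggests Phase 1 v Phases 2 and 3 combined.
- The summary describes the two later groups as "some elements of a fast-track program during a transition period, and full enhanced recovery program". Leaving out a transition group suggests Phase 1 v Phase 3.
- Section 6 (Phase 3) says the program was completed from 2018. Before and after the completed program could be Phases 1 and 2 combined v Phase 3.

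All three are possible, and the documents choose none of them.

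**Step 2. Inputs.** From the documents: three groups, alpha 0.05, N = 470. The plan has no power or error figure to reproduce. Assumed: two-sided tests, normal data with equal SD unless stated, and three splits of 470:

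- A: 235/117/118. Even accrual over four years is 470/4 = 117.5 a year, so two years for Phase 1 and one each for Phases 2 and 3.
- B: 157/157/156.
- C: 300/85/85.

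**Step 3. Chance of at least one false positive per outcome, no true difference.** If three tests were independent: 1 - 0.95^3 = 0.1426. Pairs share groups, so the true figure is lower. By simulation:

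| Tests run | A | B | C |
|---|---|---|---|
| One contrast fixed in advance (1 v 3) | 5.0% | 5.0% | 5.1% |
| All three pairs, t-test | 12.1% | 12.2% | 12.0% |
| All three pairs, Mann-Whitney | 12.3% | 12.4% | 12.0% |
| Global F test, then pairs only if significant | 5.0% | 5.0% | 5.0% |
| Kruskal-Wallis, then Mann-Whitney pairs | 5.1% | 5.1% | 4.9% |

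The rank-test rows assume a skewed stay: 2 days plus a negative binomial count (mean 4, size 3). Testing all three before-and-after readings of Step 1 gives 9.0-9.7% across the splits.

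**Step 4. Why the gate suffices with three groups.** If all phases are equal, a false pairwise claim first requires a false global result, so the chance is at most about 5%. If exactly two phases are equal, only one true null is left among the pairs, and it is tested at 0.05. Simulated with the third phase 1 SD away, the equal pair is rejected in 4.97-5.04% of runs. Holm is not needed on top.

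**Step 5. Unequal variances.** With assumed SDs of 1, 1.25 and 1.5 in Phases 1, 2 and 3 and equal means, the Student t-test of Phase 1 v 3 rejects 8.5% of the time in split A and 11.4% in split C. It stays at 5% with equal groups. With the SD order reversed it is conservative in the unequal splits (1.4-2.6%). Welch tests restore about 5%, so the Welch form is needed for the pairs as well as for the global test.

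**Step 6. Power for Phase 1 v 3 at an assumed 0.3 SD difference.**

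| | A | B | C |
|---|---|---|---|
| No gate | 76% | 75% | 68% |
| Gated, Phases 2 and 3 both changed | 72% | 70% | 65% |
| Gated, only Phase 3 changed | 67% | 70% | 57% |
| Gated, Phase 2 changed half as much | 65% | 64% | 58% |

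**The case against.** The best defence is that the plan never says all three pairs will be tested. A two-sample test of one contrast fixed in advance is sound. The outcomes are secondary, the study is retrospective, and sections 3.1 and 3.2 speak only of measuring outcomes, with no confirmatory claim. All of this stands, and it limits the grade. It does not close the gap: the summary announces a comparison of three groups, the only tools named handle two, and no pair is named. The words about appropriateness in the test sentence most naturally govern the choice between t-test and Mann-Whitney after the normality check. They supply no three-group method.

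Four stronger readings are tempting, and the documents support none of them.

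- A reader might infer that the named tests are wrong. They are not; their use across three groups is unspecified.
- A reader might infer that 12% is the error rate of this study. It applies only if all three pairs are tested.
- A reader might treat differing verdicts from the rival contrasts as an error. When the phases differ, those contrasts estimate different quantities with different precision, so disagreement between them is not an error rate.
- Section 2 hypothesises that the shift "can be implemented in a secondary-care hospital while ensuring the same safety and effectiveness for patients", and a reader might infer that a non-significant test will be taken as proof of sameness. No section says so.

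The point also makes no claim about the complication endpoints. Nor does it settle whether mobility means postoperative values or change from baseline: the summary speaks of improvement, section 3.2 lists both time points, and the same procedure works for either.

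**Conclusion.** The concern holds in a limited form. For length of stay and postoperative knee extension and flexion, the plan sets up a three-phase comparison with two-sample tests only, each at 0.05, and leaves the before-and-after contrast open. The cost is a false-positive chance of about 12% per outcome if all three pairs are tested, or about 9-10% if all three before-and-after readings are tested, against 5% for one fixed contrast or a gated procedure.

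The phase sizes are assumed, but the 12% barely moves across the splits. The t-test figures also assume normal data and equal SDs. Severity is low to moderate because every outcome concerned is secondary.

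**What to change.** In section 8.2 and the summary, replace the sentence on continuous data with wording such as:

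*Continuous outcomes are compared across the three phases by Welch one-way ANOVA, or by Kruskal-Wallis if not normal, at 0.05. Pairwise Welch t-tests or Mann-Whitney tests at 0.05 are run only if this test is significant. Every pairwise difference is reported with a 95% confidence interval.*

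If the sponsor prefers a single before-and-after contrast, the plan should fix it before analysis and state the role of Phase 2. It is then tested at 0.05 with Welch or Mann-Whitney, and the remaining comparisons are descriptive. The two routes should not be combined: a named contrast tested outside the gate plus gated pairs brings the false-positive chance back to about 7.5% per outcome.

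The cost is wording and standard procedures, with no new data. The gate lowers power for a single pair: for Phase 1 v 3 at an assumed 0.3 SD, from 68-76% to about 57-72%, depending on the split and on how far Phase 2 also changed. The single-contrast route avoids that loss but gives up formal tests of the other comparisons.
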